Open-label trials of TOP conducted in Spain (29) and in Greece (30) also provided evidence of the utility of TOP in individuals of European descent. However, a placebo-controlled study conducted in Thailand failed to show a significant advantage of TOP in reducing drinking in that population (31). The interpretation of the findings from that study is limited by the low rate of study completion (53% in the TOP group and 47% in the placebo group) resulting in a large amount of missing data. Further, there was no evaluation of adherence to the prescribed regimen. A meta-analysis of 7 randomized controlled trials (a total of 1,125 participants) compared topiramate to placebo for treating AUD(4). The largest effect for topiramate was found on the following outcomes: abstinence ($g = 0.468$, $p < 0.01$), heavy drinking ($g = 0.406$, $p < 0.01$), the liver enzyme GGT ($g = 0.324$, $p = 0.02$), and craving for alcohol ($g = 0.312$, $p = 0.07$). The authors concluded that the efficacy was greater magnitude than that of either naltrexone or acamprosate. However, despite a growing literature on the use of TOP for treating AUD, there are no published studies that have enrolled a substantial number of African-ancestry patients, so that our knowledge of the potential utility of TOP for treating AUD in AAs is non-existent.

We completed a 12-week, placebo-controlled trial of the efficacy of TOP 200 mg/day. The dosage in that study was chosen to be more tolerable than the 300-mg/day dosage used in most of the prior studies. The study enrolled 138 heavy drinkers [62.3% male, 88.4% European American (EA)] whose goal was to reduce their drinking (7). Patients were randomly assigned to receive 12 weeks of treatment with TOP (N=67, 48.6%) or matching placebo (N=71, 51.4%), together with medical management. During the 90-day pre-treatment period, patients in both groups were abstinent ~1 day/wk and drank heavily (men: ≥ 5 standard drinks; women: ≥ 4 standard drinks) on ~5 days/week. Fifty-six TOP patients (83.6%) and 61 placebo patients (85.9%) completed the 12-week treatment period ($p=0.70$). There was a main effect of medication group ($p<0.001$) and

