D.1. Overview: The proposed study, which will be registered on clinicaltrials.gov, is a two-arm, 12-week, parallel-groups comparison of TOP and placebo in reducing the frequency of heavy drinking days and increasing the frequency of abstinent days in 160 AA Veterans with AUD. We will enroll Veterans whose goal is either to reduce drinking to safe levels or stop drinking. At each visit, all patients will receive Medical Management, a manualized form of supportive care that encourages them to achieve their drinking goal (MM) (45). Random assignment to treatment group and double-blind conditions will be maintained throughout the study. Raters will be trained in the reliable use of all assessments. We will use serum %dCDT to validate patient reports of drinking.

D.2. Patients: One hundred-sixty AA men and women will be recruited using a variety of methods including clinical referrals, IRB-approved advertisements, and referral from the BHL program at the CMCVAMC. We will also obtain IRB approval to identify prospective patients using the electronic health record.

D.2.a. Inclusion Criteria: a) self-identification as AA, which has been shown to be highly correlated with genetic ancestry (in 3,636 subjects of varying race/ethnicity, only 5 (0.14%) showed genetic cluster

membership different from their self-identified race/ethnicity (46)); b) age 18 to 70 years, inclusive; c) average weekly ethanol consumption of ≥ 24 standard drinks for men or ≥ 18 standard drinks for women, with a weekly average of ≥ 2 heavy drinking days (men: ≥ 5 standard drinks; women: ≥ 4 standard drinks) during the month before screening; d) a current diagnosis of moderate or severe AUD (i.e., meeting at least 4 of 11 DSM-5 AUD criteria); e) expressed goal to reduce or stop drinking; f) able to read English at the 8th grade or higher level and without gross cognitive impairment; g) willing to nominate an individual who will know the patient's whereabouts to facilitate follow up during the study; h) women of child-bearing potential (i.e., who have not had a hysterectomy, bilateral oophorectomy, tubal ligation or are less than two years postmenopausal), must be non-lactating, practicing a reliable method of birth control, and have a negative serum pregnancy test prior to initiation of treatment; and i) willing to provide signed, informed consent to participate in the study.

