a. Overall condition at the end of treatment (for early withdrawal from the study): The Early Termination Form, indicating the patient's level of functioning at termination, will be completed by the nurse for any patients that leave treatment prematurely. The form is used to identify the reasons for early termination (e.g., non-response, adverse effects) and other relevant circumstances. Patients unable to return for the endpoint will be mailed all questionnaires (with a stamped envelope for ease of return) and then interviewed by telephone. Patients will be compensated to complete the assessments. Using this and similar methods, we have been successful in obtaining 90% of data from subjects in alcohol treatment trials.

D.5.b.3. Areas assessed at intake and end of treatment:

a. Alcohol use patterns: The Timeline Follow-back (TLFB) (50) will be used to estimate past 90-day drinking at intake and at every treatment visit going back in time from the last assessment. The TLFB is reliable and valid when used by trained interviewers.

b. Alcohol-related problems: The Short Index of Problems (SIP), a 15-item instrument, was derived from the 50-item DrInC (32) and measures a single factor of alcohol-related problems (51). It proved to be sensitive as a measure of treatment outcome in our completed trial of TOP (7). As in that study, SIP scores will be used to describe the pretreatment alcohol-related problem severity of the sample and for concurrent validation of self-reported drinking during treatment and follow-up.

D.5.b.4. Areas assessed at each visit

a. Medication usage: The primary measure of medication adherence is recording of the pills dispensed and those taken by the patient from blister cards. The blister cards are prepared by the research pharmacist to be given as weekly packets. Blister cards have several advantages over pill counts, MEMS caps or riboflavin, including low cost, direct feedback to the patient regarding adherence, and ease of delivery (52). The use of riboflavin has been particularly questioned as a measure on adherence (53). Patients will be asked to return the unused portion of study medication at each visit. They will be compensated \$5 for each visit at which they return the medication container.

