D.7. Data Analyses: The study will use the web-based direct entry data management system of the Penn Center for Studies of Addiction, with data stored on secure servers at the CMCVAMC. This arrangement has been approved and is described in a Memorandum of Understanding between the CMCVAMC and the Perelman School of Medicine at Penn. Interview data and self-report data are entered directly onto computers by research staff and/or subjects under supervision by staff. A range of checks for the validity of responses (including field validation to ensure that no out-of-range or otherwise invalid responses are accepted), and form validation (to ensure that logically impossible responses to different questions are not accepted) are built into this entry process. After entry, the research staff performs a brief review to ensure that the form has been completed. On completion of this review, the technician transmits the data (in 128-bit encrypted form) over the Internet to the DMU data servers. After a series of online reviews, the data are archived on the servers without protected health information. Audit logs record any modification to the original entry. Various levels of password protection will allow access to the data by members of the research team.

An important initial consideration will be to identify baseline differences between groups that may have occurred despite the use of block randomization. Prior to analysis, the distribution of outcome data will also be examined to determine the need for transformation and whether parametric analytic methods can be used.

D.7.a. To examine the effects of TOP treatment on the number of heavy drinking and abstinent days during the final six weeks of treatment (Specific Aim 1). The two primary outcomes, which will be measured using the TLFB, are the frequency of heavy drinking days (≥ 5 standard drinks in a day for men and ≥ 4 in a day for women), a sensitive, clinically relevant measure in alcohol treatment trials, and the frequency of abstinent days (56). An attempt will be made to evaluate outcomes for all patients irrespective of whether they continue to receive treatment, so that the analysis of all outcomes will be based on all of the data available for all randomized patients. Secondary outcomes for Aim 1 will include the severity of alcohol-related problems (i.e., SIP score) and %dCDT, which will be analyzed using models similar to those described below for the primary outcomes.

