The two medication groups will be compared on weekly number of heavy drinking days and weekly number of abstinent days using mixed effects models for count responses, fitted using PROC GLIMMIX in SAS and the HGLM module of the HLM7 program (57). Estimates of effects over the final six weeks from the models, with associated standard errors and confidence intervals, will be used to test the primary hypotheses, i.e., that TOP treatment will reduce heavy drinking days and increase abstinent days more than placebo during the final six weeks of treatment. The models will include covariates for linear and quadratic time trends, as appropriate for model fit. The random effects will include a random intercept and, if necessary, residual autocorrelations, random slopes, or other specifications will be used. Although the primary contrasts will concentrate on the final six weeks, these models utilize all available data from all patients, so the analyses follow the intent-to-treat principle.

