D.7.c. To examine the persistence of effects of TOP treatment on the number of heavy drinking and abstinent days during a six-month post-treatment follow-up period (Specific Aim 3). We will use linear mixed models to examine medication group differences in percent heavy drinking days, percent days abstinent, SIP, GGTP, and %dCDT across the treatment and post-treatment periods. The 12-week treatment period, along with the 3-month and 6-month follow-up periods will be included in the analysis to determine whether the change in outcomes from treatment to follow-up differ by medication group. The models will include study period (treatment period, 3-month follow-up, 6-month follow-up), treatment group (TOP, placebo) and the interaction between these two factors to test for differences between study periods, treatment groups, and the change in the difference between groups across study periods. Baseline (pretreatment) values for each outcome will be included as covariates in modeling the respective outcome. The outcomes for Aim 3 are considered exploratory. We will also explore the persistence of TOP effects using the primary SNP identified in Aim 2. That is, we will conduct a pharmacogenetic analysis of the persistent effects of TOP, similar to our analysis of heavy drinking in EAs, where rs2832407*C homozygotes treated with TOP had robust reductions in heavy drinking during the six-month post-treatment period (10).

D.7.d. Dropout and Missing Data: We will base the primary relative efficacy comparisons in the trial on mixed effects models utilizing all data provided by participants. In our completed TOP trial, we saw limited dropout (8% to the start of the final six weeks, and 4% thereafter). We will assess the sensitivity of our assumption that missing data are ignorable by running models that address missingness in different ways. For mixed effects models, pattern mixture models test for differences in regression estimates across patterns of missing data, and shared parameter models allow for correlated random effects for the primary responses and the week-to-week binary indicators of missing/complete data (57). Semi-parametric regression models use inverse probability weighting to extend the validity of GEE models, and provide a different type of sensitivity analysis for the mixed effects models (59). All of these modeling approaches require certain model assumptions, so we will compare the results of the analyses over a range of such assumptions.

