D.7.e. Adherence: To assess the sensitivity of the results of the analyses described above to non-adherence, the models described above for our primary and secondary outcomes will be extended using instrumental variable approaches. Under some assumptions, these analyses will yield estimates of the intervention effects that would have been seen in a study with full adherence. To analyze data using a single overall measure of adherence (e.g., 80% of assigned medication taken over the 12 weeks of treatment), we will use the methods of Nagelkerke et al. (60). We will also examine longitudinal extensions of these methods, looking at weekly adherence to medications as a time varying measure (61).

D.7.f. Adequacy of Sample Size for Specific Aim 1: The analyses described above make use of all data provided by all patients to estimate models from which contrasts restricted to the final six weeks will test the TOP effect on days of heavy drinking and abstinent days (Specific Aim 1). Power for the contrasts will be determined by the patterns of outcomes in the final six weeks, so power estimates are based on weeks 7

through 12 as a 6-week trial, with adjustments for loss to attrition between baseline and week 6. Based on our prior study (7) we anticipate 92% retention through the first six weeks for each group, yielding 74 available per group at the end of week 6, an additional 4% loss due to dropout across the final six weeks, and a within-subject correlation of about 0.6. The methods of Hedeker et al show that we will have 80% power for a TOP main effect size of $d=0.40$, 0.43 , and 0.46 , for within-subject correlations of 0.5 , 0.6 , and 0.7 , respectively, at a corrected alpha level of 0.025 (62). In [name] et al, the effect sizes for heavy drinking days in weeks 7 through 12 varied between $d=0.52$ and $d=0.62$, so the sample size should be adequate to detect similar effects in the current study (7).

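### The primary Aim 1 models do not prespecify adjustment for pretreatment drinking, although it is collected at intake and the exploratory Aim 3 models use it; adding it costs no patients or data and gains precision.

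*Combined protocol and SAP*

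**What the plan says.** Section D.7.a compares the arms on weekly heavy drinking days and weekly abstinent days with mixed effects count models, and tests the treatment effect over the final six weeks. On covariates it says: "The models will include covariates for linear and quadratic time trends, as appropriate for model fit". It adds a random intercept and, if needed, further random effects or residual autocorrelation. Pretreatment drinking is not mentioned.

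Three other places bear on this:

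- Section D.5.b.3: the Timeline Follow-back "will be used to estimate past 90-day drinking at intake and at every treatment visit". The pretreatment measure therefore exists, from the same instrument that yields both primary outcomes.
- Section D.7.c (Aim 3): "Baseline (pretreatment) values for each outcome will be included as covariates in modeling the respective outcome". The same section says: "The outcomes for Aim 3 are considered exploratory".
- Section D.7, opening text: an early step is to "identify baseline differences between groups that may have occurred despite the use of block randomization". What follows if differences are found is not stated.

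The block randomization in section D.3.c balances on treatment goal, not on baseline drinking.

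**The concern.** The plan prespecifies baseline adjustment for its exploratory models and leaves it out of its confirmatory ones. Two things follow.

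**Precision.** Patients differ in habitual drinking before treatment. Whatever part of that difference carries through to weeks 7-12 stays in the standard error of the primary contrast unless baseline is in the model. The random intercept does not remove it. It describes the between-patient variance, but the contrast between arms is still made against that variance.

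**An open rule.** Because the baseline check in D.7 has no stated consequence, a reader cannot tell whether baseline enters the primary test always, never, or only after an imbalance is seen. Under the last reading the observed data would choose the primary model. A fixed rule closes this whatever the size of the correlation.

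**Working it through.** **Inputs from section D.7.f.** 92% retention of 80 per arm to week 6 (80 × 0.92 = 73.6, given as 74); a further 4% loss (74 × 0.96 = 71); six weekly measures; within-subject correlation ρ about 0.6; alpha 0.025. Sidedness is not stated. Two-sided is taken because it reproduces the plan; one-sided gives about 88% power.

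**Step 1: the plan's own figure.** For the mean of six equally correlated weeks,

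SE = √[(2/n)(1 + 5ρ)/6] = √[(2/71)(4.0/6)] = 0.137.

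Detectable d at 80% power = (2.241 + 0.842) × 0.137 = 0.422, against the plan's 0.43. For ρ = 0.5 and 0.7 the same formula gives 0.395 and 0.448 (plan: 0.40 and 0.46). Power at the plan's three effects is 81.0%, 81.5% and 82.2% by the normal approximation, or 80.3%, 80.7% and 81.5% by the noncentral t. The plan's 80% is reproduced.

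**Step 2: add the baseline covariate.** In a linear approximation the SE is multiplied by √(1 − r²), where r is the correlation between pretreatment drinking and mean drinking in weeks 7-12. **The documents do not give r; 0.2 to 0.5 is an assumption.** It is not the plan's 0.5-0.7, which is the correlation among on-treatment weeks. The entry criteria (section D.2.a), which require patients "with a weekly average of ≥ 2 heavy drinking days" and set a minimum weekly consumption, narrow the baseline range and may lower r.

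Results for ρ = 0.6 and n = 71 per arm, where power = Φ(d/SE − 2.241):

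| r | Detectable d | Power at 0.406 | at 0.43 | at 0.468 | at 0.52 | at 0.62 |
|---|---|---|---|---|---|---|
| unadjusted | 0.422 | 76.5% | 81.5% | 88.0% | 94.0% | 98.9% |
| 0.2 | 0.414 | 78.3% | 83.2% | 89.3% | 94.9% | 99.1% |
| 0.3 | 0.403 | 80.6% | 85.3% | 91.0% | 95.9% | 99.4% |
| 0.4 | 0.387 | 83.9% | 88.1% | 93.1% | 97.1% | 99.6% |
| 0.5 | 0.366 | 88.1% | 91.6% | 95.6% | 98.4% | 99.9% |

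The effects 0.52 and 0.62 are the prior-trial range in D.7.f. The values 0.406 (heavy drinking) and 0.468 (abstinence) are the pooled effects from the meta-analysis cited in section B.1.b. They may not be on the same scale as the weekly d.

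In sample-size terms the gain is 1/(1 − r²): 1.10 times the patients at r = 0.3 and 1.33 times at r = 0.5.

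**Step 3: does this carry over to counts?** Two simulations of heavy drinking days were run with 71 per arm. Their data models are assumed, not taken from the documents.

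- Six-week totals out of 42 days, baseline truncated at 2 or more heavy drinking days a week, quasi-Poisson with and without log baseline, 1,000 trials per setting. Adjustment cut the variance by 2%, 7%, 16% and 25% at observed r = 0.19, 0.30, 0.43 and 0.53. The linear formula predicts 4%, 9%, 19% and 28%, so step 2 is slightly optimistic.
- A log-link model with robust standard errors, 600 runs. Adjustment cut the SE of the log rate ratio from about 0.127 to 0.122 and 0.113 at r = 0.28 and 0.47, and raised power from about 76% to 80% and 88%. Rejection under the null stayed near 0.025 (0.018 to 0.033). At zero correlation there was no gain and no visible loss.

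**The case against.** **The test is valid and well powered as it stands.** True. At the effects the plan expects, unadjusted power is 94-99% and adjustment adds little.

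**The case leans on the smaller pooled effect.** The same meta-analysis gives 0.468 for abstinence, which is above the detectable 0.43. For that outcome power is 88.0% unadjusted and 89-96% adjusted. This stands: the gain matters less for abstinent days than for heavy drinking days.

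**r is unknown and may be low.** At r = 0.2 to 0.3 the gain at d = 0.43 is only 2 to 4 percentage points, and nothing in the documents supports r = 0.5 in particular. This also stands, and is why a range is shown.

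**The simulations do not fit the plan's weekly mixed models and cover only heavy drinking days.** Correct. They support the direction and rough size of the gain for that outcome, not exact figures for all four outcomes.

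**Baseline may already be in the model.** D.7.a says the models use all available data, which could be read as entering pretreatment weeks as responses. The text does not say so. If that is meant, it has to be written, because baseline should not then also be added as a covariate.

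**A covariate on the log scale fails when baseline abstinent days are zero.** This does not apply to the weekly frequency itself, which is what the fix proposes.

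**Conclusion.** The concern holds. The primary models leave out a covariate that is already collected and that the plan's exploratory models use, and the role of the baseline check is undefined. Nothing in the plan's power statement is wrong.

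Under the assumed r of 0.2 to 0.5, adjustment lowers the detectable d from 0.42 to 0.41-0.37 and adds about 2 to 10 percentage points of power at d = 0.43, probably a little less in a count model. The benefit is small if the prior-trial effects recur. It is useful if the effect is nearer the pooled 0.406, where power goes from 76.5% to 78-88%. That possibility deserves weight because the prior trial's sample was 88.4% European American and the plan itself argues that response may differ between populations. The change is worth making but is not essential. Confidence in the direction is high; confidence in the size is moderate, since r is not documented.

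**What to change.** 1. In D.7.a, prespecify the patient's pretreatment weekly frequency of the modelled outcome (heavy drinking days or abstinent days, from the intake Timeline Follow-back) as a fixed covariate in each primary model, whatever the observed balance. State its functional form and the scale of the reported effect, because in a count mixed model the adjusted effect is conditional on baseline.
2. State the same for baseline SIP score and baseline %dCDT in the secondary models.
3. In D.7, say that the baseline comparison of the arms is descriptive and does not select covariates.
4. If pretreatment weeks were meant to enter as responses, say so in D.7.a in place of item 1.

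The cost is a few sentences in the analysis plan and one parameter per model. No new data or visits are needed, and the sample size does not change.

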D.7.b. To explore the moderating effects of variation at *GRIK1* and other glutamate system genes on the efficacy of TOP 200 mg/day in reducing the frequency of heavy drinking and increasing the frequency of abstinent days (Specific Aim 2). Specific Aim 2 will be addressed by including a binary indicator of the SNPs identified as being associated to sustained heavy drinking through the MVP beta test project in the models described above for testing Specific Aims 1. These models will include the main effect of the SNP indicator and its interaction with medication group and time. Analyses will be conducted and results described as above. To identify candidate variants to test in the pharmacogenetic analyses, we will select SNPs in *GRIK1* and *GRIK2* (the genes that encode the GluK1 and GluK2 kainate subunits, on which TOP's effects are most potent and selective (39), using data from the MVP project, or alternatively from the GWAS that we completed on 3,318 AAs (11). We will select the 10 SNPs in these genes that yield the smallest p-values (ideally, but not necessarily, the p-values for these SNPs will be smaller than the p-value that is typically used to determine genomewide significance: $p < 5.0 \times 10^{-8}$). We will test for moderating effects by starting with the most significant SNP and continuing until one shows significance, with the value of α adjusted each time to reflect the number of comparisons (such that the tenth SNP would be tested using $\alpha = 0.005$). We will also construct a gene-based analysis, considering common variation mapped to genes that are implicated as being associated to sustained heavy drinking in the MVP sample or alcohol dependence in our sample (11). We will use the approach developed by Lin and et al. (58), where the interaction effect between an environment (treatment in our case) and all the SNPs within a gene can be considered in a unified framework. Analyses will be conducted and results described, as above. In particular, separate estimates and confidence intervals will be reported for the TOP effects in the two levels of each binary genotypic indicator. The outcomes for Aim 2 are exploratory.

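### Exploratory Aim 2 (minor): read as 0.05/k until the first hit, the SNP testing ladder carries up to a 13.8% chance of a false moderator on one outcome, not the 5% that 0.005 for ten tests suggests

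*Combined protocol and SAP*

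**What the plan says.** Section D.7.b sets the candidates: "We will select the 10 SNPs in these genes that yield the smallest p-values". The p-values come from the Million Veteran Program analysis or the investigators' earlier GWAS, so the order does not depend on trial data. Testing for moderation starts at the top of the list, "continuing until one shows significance, with the value of α adjusted each time to reflect the number of comparisons". One level is given as an example: 0.005, for the last of the ten. The levels for the first nine SNPs are not printed, and no familywise error rate is stated for the sequence.

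The aim covers two outcomes, heavy drinking days and abstinent days. D.7.b does not say which of them decides that a SNP has passed. It does promise that "separate estimates and confidence intervals will be reported for the TOP effects in the two levels of each binary genotypic indicator", and it adds: "The outcomes for Aim 2 are exploratory".

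The result is used again in D.7.c: "We will also explore the persistence of TOP effects using the primary SNP identified in Aim 2". That section also says "The outcomes for Aim 3 are considered exploratory". D.7.g accepts that the sample may be too small for definitive analyses of Aims 2 and 3, and expects the effect-size estimates to guide later topiramate studies.

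**The concern.** A rule that goes on testing after each failure must budget alpha over every test that might be made. Dividing by the number of tests made so far does not do this: the first SNP alone uses a full 0.05, and each later SNP adds to it.

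The rule is none of the usual procedures:

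- Bonferroni would use 0.005 for all ten SNPs.
- Holm would order by the trial's own p-values, start at 0.005 and then relax.
- Fixed-sequence testing would use 0.05 throughout but stop at the first failure.

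Stopping at the first success does not help when all ten SNPs are null, because the first success is then already the false finding.

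The SNP that passes becomes the single SNP in the pharmacogenetic part of Aim 3, whose hypothesis in section A concerns a genetically responsive subgroup. A false pick would define the wrong subgroup, and its effect estimate could be taken into the design of later studies. A reader who sees 0.005 for ten SNPs may assume 5% protection.

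**Working it through.** **Inputs**

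- Ten SNPs in externally fixed order, with a stop at the first significant one (D.7.b).
- Tenth level 0.005 (D.7.b).
- Base level 0.05: inferred. It fits 0.05/10 = 0.005 exactly. It also fits D.7.f, where two primary outcomes are tested "at a corrected alpha level of 0.025", i.e. 0.05/2. A base of 0.025 would give 0.0025 at the tenth SNP, which does not match.
- Correlation between SNP tests: not given, so a range is shown.

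**Levels.** α_k = 0.05/k gives 0.05, 0.025, 0.0167, 0.0125, 0.01, 0.0083, 0.0071, 0.0063, 0.0056, 0.005. Their sum is 0.05 × (1 + 1/2 + … + 1/10) = 0.05 × 2.929 = 0.146, which is the upper bound under any dependence.

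**No true moderator, independent tests.** The chance of at least one false hit after m SNPs is 1 − ∏(1 − 0.05/k), k = 1 to m.

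| SNPs tested | Chance of a false moderator |
|---|---|
| 1 | 5.0% |
| 2 | 1 − 0.95 × 0.975 = 7.4% |
| 4 | 10.1% |
| 10 | 13.8% |

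For comparison, ten SNPs all tested at 0.005 give 1 − 0.995^10 = 4.9%.

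**No true moderator, correlated tests.** With equally correlated two-sided normal statistics over all ten SNPs:

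| Assumed correlation | Ladder 0.05/k | Levels 0.05/(2.929k) |
|---|---|---|
| 0 | 13.8% | 4.9% |
| 0.3 | 12.6% | 4.6% |
| 0.5 | 10.8% | 4.0% |
| 0.8 | 7.3% | 2.7% |
| 0.95 | 5.4% | 1.9% |

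**One true moderator, independent tests.** If it ranks first with power P at 0.05, a false pick requires it to be missed and one of the other nine to pass: (1 − P) × [1 − ∏(1 − 0.05/k), k = 2 to 10] = (1 − P) × 0.0926. If it ranks second, a false pick can also occur at the first SNP, with probability 0.05.

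| Power of the true SNP at 0.05 | Ranked first | Ranked second |
|---|---|---|
| 80% | 1.9% | 6.9% |
| 50% | 4.6% | 9.0% |
| 30% | 6.5% | 10.2% |

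**Two outcomes.** On a 0.05 base, 0.005 counts ten SNPs but not two outcomes; counting both gives 0.05/20 = 0.0025. If either outcome could select the SNP and the two were independent, the rate with no true moderator would be 1 − (1 − 0.138)² = 25.7%. Correlation between the outcomes would lower this.

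**The case against.** The strongest reply is that no printed figure is wrong. The only one, 0.005, equals 0.05/10, and the plan never claims a 5% familywise rate. The text also says that alpha changes at each step, so a careful reader can see that earlier SNPs face looser levels. That stands: this is a weakness in the choice of procedure, not a slip in calculation, and the 5% benchmark is inferred.

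Second, 13.8% is close to the worst case for one outcome. Ten top SNPs from only two genes, with no pruning for linkage described, may well be correlated, and a true top-ranked moderator lowers the risk further. This also stands, and is why a range is given.

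Third, Aims 2 and 3 are declared exploratory and possibly underpowered, so favouring sensitivity for the best candidate is defensible. That argument could justify making no adjustment. It does not justify presenting an adjustment for the number of comparisons that fails to cover the comparisons made, least of all when the result selects the subgroup for the next analysis.

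Finally, the questions of which outcome selects the SNP and what happens if none passes are gaps in specification. They do not support the 13.8% figure and are raised only because the same sentence of the plan needs editing.

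**Conclusion.** The concern holds, as a minor point. Read as 0.05/k, the ladder does not keep the chance of a false moderator at 5% once a second SNP is tested. The 13.8% figure assumes ten SNPs with no moderating effect, independent tests and a single outcome. With the positive correlations examined, the rate lies between 12.6% and 5.4%. With one true moderator ranked first or second, the chance of picking a false SNP runs from 1.9% to 10.2% over the powers considered. The 0.05/k reading and the 5% benchmark are inferences from the printed 0.005 and from the Aim 1 correction. The primary analysis of Aim 1 is not affected.

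**What to change.** In D.7.b, replace the ladder with one of these:

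1. **Weighted Bonferroni.** Keep the external ranking and the stop at the first hit, with pre-specified levels 0.05/(2.929k): 0.0171, 0.0085, 0.0057 and so on down to 0.0017. They sum to 0.05, so the rate cannot exceed 5% under any dependence. The first SNP to pass is the primary SNP for Aim 3.
2. **Holm over all ten SNPs**, first step 0.005. If several pass, the one ranked highest externally is the primary SNP for Aim 3.

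With either option:

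- Say what the pharmacogenetic part of Aim 3 does if no SNP passes.
- Name heavy drinking days as the single selection outcome, or count both outcomes (halve the weighted levels, or start Holm at 0.0025).
- Report the SNP-by-treatment interaction with its confidence interval for all ten candidates, including those ranked after the first hit. This adds to the genotype-level estimates already promised.

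If the present ladder is kept, print all ten levels, state that no 5% familywise level is claimed, and give the 13.8% figure with its assumptions.

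The change is to analysis-plan wording only. The cost of options 1 and 2 is power for the top-ranked SNP, shown below at the first-step levels. The relative loss is larger when starting power is low, which matters in an aim that D.7.g already regards as possibly underpowered.

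| Power at 0.05 | At 0.0171 | At 0.005 |
|---|---|---|
| 80% | 66% | 50% |
| 30% | 17% | 9% |
| 20% | 10% | 5% |
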